## **5. DATA ANALYSIS AND DATA MONITORING**

### **Primary Outcomes:**

1. Assessment of safety and tolerability of NanoDOX® Hydrogel in AD subjects on lesional and non-lesional (clinically normal appearing) skin, including pain and dermatologic/skin toxicity (incidence, severity, frequency, duration and causality) in lesional skin at target site (NanoDOX® Hydrogel). 2. Improvements rate of IGA and EASI score in lesional skin treated with NanoDOX® Hydrogel before and after treatment. We will quantify clinical improvement as: IGA (0-4) fold improvement from baseline; percent of subjects reaching EASI50 (50% improvement over baseline) or EASI75 (75% improvement over baseline) at each time point post treatment (V2 and V4). 3. Objective Clinical improvement based on digital photography scoring (0-4 scale and size of active lesion), measured as fold improvement over baseline at each time point (V2 and V4).

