**Study procedures & methods**

- **Disease status assessment:** **1)** Investigator Global Assessment (IGA), which will provide information of the overall disease (four point scale: clear, mild, moderate, severe) and it is the score requested by FDA for clinical study and **2)** Eczema Area and Severity Index (EASI), a well-accepted and validated scoring system for general disease activityxiv. It is the sum of the intensity scores (0 to 3) for four signs: erythema, induration, excoriation, lichenification and it is recorded for targeted treatment areas as well as four regions of the body (i.e., head, trunk, lower and upper extremities). Data will be reported as percent change in EASI score from baseline and each visit. Proportion of participants achieving EASI50 and EASI75 will be determined at each study timepoints. The presence or absence of skin irritation (e.g. macular/papular eruption), redness, atrophy and telangiectasia will be noted at each study visit.  
**3)** The pruritus intensity will be assessed using the 5-D Pruritus Scale. The pruritus categorical scale is a 4-point scale commonly used in clinical studies of AD and has less of a “middling” effectxv The scale is rated as follows: 0: absence of pruritus; 1: mild, pruritus (occasional slight itching/scratching); 2: moderate pruritus (constant or intermittent itching/scratching that does not disturb sleep) and 3: severe pruritus (bothersome itching/scratching that disturbs sleep).
- **Digital pictures:** A digital picture will be taken with a dedicated digital camera. The pictures will be labeled with the subject’s study ID and date. Pictures will not include identifying information (e.g. facial features, tattoo, etc). Pictures will be taken at a distance for easy identification of the anatomical area and closer to better capture clinical changes. Digital photographs will be used to record the location and monitor the size of target lesions. Quantification of change in size will be obtained using Image J software.  
At conclusion of the study, two trained physicians/dermatologists will be asked to score clinical pictures (0-4 scale, clear, mild, moderate, severe) in a blind fashion (*i.e.*, pictures will be de-identified and presented randomly/ not in chronologic order). This would allow to objectively confirm the clinical score taken during the study.

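### Fold improvement in IGA, photograph score and lesion size has no formula and, in its usual sense, no value at clearance; the IGA and photograph scales are also inconsistent

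*Combined protocol and SAP*

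**What the plan says.** Section 5, Primary Outcomes, item 2 concerns "Improvements rate of IGA and EASI score in lesional skin treated with NanoDOX". The global assessment is summarised as "IGA (0-4) fold improvement from baseline". EASI, in the same sentence, is summarised as "percent of subjects reaching EASI50 (50% improvement over baseline") or the corresponding 75% threshold. Item 3 covers two photographic measures ("0-4 scale and size of active lesion"), "measured as fold improvement over baseline at each time point (V2 and V4"). No section gives a formula for the fold measure, its direction, a rule for a zero value or a summary statistic.

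Section 3, Study procedures & methods, adds the following:
- Lesion size: "Quantification of change in size will be obtained using Image J software". The change measure is not defined.
- EASI: "Data will be reported as percent change in EASI score from baseline and each visit". It is recorded for the target area and for four body regions.
- IGA: a score "which will provide information of the overall disease (four point scale: clear, mild, moderate, severe").
- Photographs: a 0-4 range carrying the same four labels.

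Section 2, Inclusion Criteria, gives an IGA range of 1-2 under moderate to severe disease.

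Clearance is provided for. Study Design lets treatment end at complete clearance, and Visit 2 sets out procedures if the treated area has resolved by then. Visit 2 is one of the two time points named for the primary outcomes.

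The analysis text after Secondary Outcomes sets the decision rule (6 or more EASI50 responders in 15), tabulates IGA from baseline to visit 4, and applies a Wilcoxon signed-rank test to the blinded pre/post evaluation.

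**The concern.** Fold improvement usually means baseline divided by follow-up. On that reading the best possible result, a cleared lesion, cannot be scored. Someone must then omit those subjects or choose a substitute value, and with no rule in the plan that choice could be made after the data are seen, in an open-label, single-arm study. For lesion size, a lesion that has almost gone gives a very large ratio that can dominate a mean. On an ordinal score, the ratio also values equal one-grade gains unequally.

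The scale problem is separate and remains whichever metric is used. If a number has no agreed label, neither a ratio nor a change in grade has a fixed meaning. It is also unclear whether the primary IGA describes the whole patient or the treated lesion.

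**Working it through.** **The plan's own figure.** The only design figure is the power of the EASI50 rule. The exact binomial gives P(X ≥ 6 | n = 15, p = 0.6) = 0.9662, which agrees with the stated value of over 96%. The fold measure does not enter this calculation.

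**Three readings of the fold measure** (b = baseline > 0, f = follow-up):
- b/f: undefined at f = 0. One-grade gains are unequal: 4 to 3 is 4/3 = 1.33; 2 to 1 is 2/1 = 2.00.
- f/b: defined, and 0 at clearance.
- (b − f)/b: defined, and 1 at clearance.

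Failure at zero therefore belongs to b/f alone. It applies to lesion size whatever the scale. It applies to the photograph score, and to a target-lesion IGA, if clear is scored 0. It would seldom arise for an overall-disease IGA, because treatment covers only an area the size of an index card.

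**Near clearance.** With 50%, 10%, 1% or 0.1% of the area left, b/f is 2, 10, 100 or 1000. On a 0-4 integer score, b/f cannot exceed 4 while it is defined. Only lesion size is unbounded.

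**Lesion-area illustration.** The response patterns and the use of a mean are assumptions. Of 15 subjects, 10 halve their area (2.00-fold) and 5 do as shown:

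| The other 5 | Mean fold | Median fold | Mean percent change |
|---|---|---|---|
| fall by 75% | (10×2 + 5×4)/15 = 2.67 | 2.00 | −(10×50 + 5×75)/15 = −58.3% |
| keep 1% | (20 + 5×100)/15 = 34.7 | 2.00 | −66.3% |
| keep 0.1% | (20 + 5×1000)/15 = 334.7 | 2.00 | −66.6% |
| clear | 20/10 = 2.00, only 10 subjects | 2.00 | −(500 + 500)/15 = −66.7% |

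**Score illustration, 0-3 (assumed).** Ten subjects go 3 to 2 and five go 2 to 1: mean fold (10×1.5 + 5×2)/15 = 1.67, mean change −1.00 grade. If the five clear instead, mean fold is 1.50 in 10 subjects, while mean change is −(10×1 + 5×2)/15 = −1.33 grades.

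**How often a zero would arise.** The documents give no clearance rate. With assumed rates of 5%, 10% and 20%, 1 − (1 − p)^15 gives a 0.537, 0.794 and 0.965 chance of at least one undefined ratio in 15 subjects.

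**Scales set side by side.** Study procedures has four IGA labels for overall disease; Primary Outcomes has IGA 0-4 in treated lesional skin. For photographs both sections say 0-4, so the mismatch lies within Study procedures: five values, four labels. With clear = 0 and whole numbers rising, four labels fit 0-4 in four ways:

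| Clear, mild, moderate, severe | Moderate to mild, fold | Moderate to mild, grades | Severe to clear, grades |
|---|---|---|---|
| 0, 1, 2, 3 | 2.00 | −1 | −3 |
| 0, 1, 2, 4 | 2.00 | −1 | −4 |
| 0, 1, 3, 4 | 3.00 | −2 | −4 |
| 0, 2, 3, 4 | 1.50 | −1 | −4 |

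In every row moderate is 2 or 3 and severe is 3 or 4, so an IGA of 1-2 does not describe moderate to severe. Numbered 1-4 from clear, 1-2 would mean clear to mild. A reversed numbering (severe = 1, moderate = 2) would fit, but no section states one, and it would also reverse the direction of the ratio.

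**The case against.** The strongest reply is that the text never chooses baseline divided by follow-up. The plan uses relative change elsewhere: percent change for EASI, percent thresholds for EASI50 and EASI75, and a worsening of more than 50% in the target-lesion score under Stopping Criteria. On that reading nothing fails at zero. This stands in part: the basic defect is the missing definition, and the consequences follow only if the usual meaning is applied. But the plan writes percentages for EASI and fold for IGA in the same sentence, so it does not settle the matter for IGA, photographs or size.

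It is also fair to say that most of the exposure is already covered. The IGA tabulation needs no ratio. Nor does the Wilcoxon test on the blinded evaluation, which from Study procedures is the photograph scoring. That stands for IGA and photographs; neither covers lesion size.

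The illustrations depend on assumed data and an assumed mean; the median is 2.00-fold in all four area cases. The four numberings are constructions, and a fifth label dropped from the text is an equally simple explanation. Both points stand. The section-to-section conflict is visible without them.

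A reader might infer more than the documents support:
- That all three measures blow up near clearance. Only lesion size does.
- That subjects who clear will be excluded. No section says so.
- That the go-ahead decision is compromised. It rests on EASI50 and does not use the fold measure.
- That the EASI region is left open. Study procedures records both target-area and body-region EASI and the decision rule names neither, but Primary Outcomes already specifies treated lesional skin. Only a cross-reference is lacking.

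**Conclusion.** The point holds in a limited form. Three primary measures rest on an undefined term whose usual meaning gives no value at an outcome the protocol provides for. The practical effect falls mainly on lesion size, which has no other stated analysis and whose ratio is unbounded near clearance. IGA and photograph scores are less exposed, and the 6-of-15 rule and its power of 0.966 are unaffected.

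The scale inconsistency is real and independent of the metric: four-point overall IGA against 0-4 lesional IGA, four labels on a 0-4 photograph range, and an eligibility range that does not fit the labels numbered upward from clear as 0 or 1. Which scale or range is right cannot be decided from the documents; the sections must be reconciled.

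Confidence is high that the definition is missing and the scales conflict. The size of any distortion is unknown; the worked examples show direction only. This should be corrected before analysis, but it does not threaten the trial's main conclusion.

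**What to change.** - **Primary Outcomes, metric.** Use percent change from baseline for lesion area, as Study procedures already does for EASI. For IGA and photograph score use change in grade from baseline, as a shift table, with the proportion clear. A one-sentence formula with a zero rule would be the minimum repair, but the proposed measures avoid both the zero problem and the unequal weighting of grades.
- **Scale.** Adopt one scale with one label per number for IGA and photographs, and reconcile Inclusion Criteria, Study procedures & methods and Primary Outcomes to it. The sponsor should set the eligibility range and decide whether the primary IGA is overall or target-lesion.
- **Decision rule.** Add a cross-reference to Primary Outcomes so that the EASI50 and EASI75 rule is read as the treated-area score.

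The cost is wording changes and, at most, one extra data field at existing visits if a target-lesion IGA is wanted and not already captured. No visits, readers or subjects are added.

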### **Secondary Outcomes:**

1. Improvements of itch score (0-5 scale) in lesional skin, before and after treatment at each time point. 2. Will evaluate Staphylococcal Aureus rate of colonization (positive or negative), difference in number of growth (0 to 3+++ ) and antibiotic sensitivity pre and post treatment. Doxycycline could have an effect on AD lesions just by reducing the Staphylococcal Aureus colonization. By integrating these findings with clinical outcomes, drug penetration and molecular changes we will be able to start to address this question. 3. Improvement of barrier function in non-lesional (normal appearing) and lesional skin pre and post treatment (V1 to V3). We will expect that clinical improvement parallels with improvement of barrier function, such as reduced TEWL, increased stratum corneum hydration and reduced pH in active treatment areas. On the other hand, worsening of the measurement will suggest damaging effect of the treatment on the skin, which could be indication of subclinical irritation induced by the treatment and/or vehicle.

The purpose of this study is a proof of concept. We are adopting a similar strategy to Phase II cancer trials that seek a clinically significant response. Using exact binomial methods, we shall obtain point and interval estimates for the fraction of subjects who respond as (a) At least EASI 50% by visit 2 or 4 and (b) At least EASI 75% by visit 2 or 4. We shall also tabulate the IGA score from baseline to visit 4. We would consider 6 or more responses (a) in 15 subjects as promising. The probability of declaring a promising result when the true response rate is 60% or higher is over 96% (power).

Side effects and baseline characteristics will be tabulated qualitatively. The blinded pre-vs post evaluation will be analyzed for IGA scores by the Wilcoxon sign-rank test.

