## 2. CHARACTERISTICS OF THE RESEARCH POPULATION

**Number of subjects** We intend to have 15, non-pregnant, non-lactating women and men of any race and ethnicity, ages 18 to 65 yrs, who are generally healthy except for atopic dermatitis diagnosed by the US Consensus criteria complete this study. This may require enrolling up to 30 subjects depending on retention rates and dropouts. Patients can have other allergic conditions such as asthma, allergic rhinitis, food allergies, etc. All AD subjects must have

moderate-severe AD as defined at screening by an Eczema Area and Severity Score (EASI)  $\geq$  10.

**Gender of subjects** We will be recruiting both male and female subjects

**Age of subjects** We will be including subjects between the ages of 18 and 65 years.

**Racial and Ethnic Origin** We will not have any restrictions based on racial or ethnic origin. We based our target research population racial and ethnic distribution on the data of the 2000 United States Census for the Alachua Area.

**Vulnerable subjects** We will not be targeting vulnerable subjects, however staff and students of UF and Shands may be enrolled as part of the general population with AD

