**3. METHODS AND PROCEDURES**

**Study Design.** We will perform a 6 weeks, pilot, investigator-initiated, single-center, open-label clinical study to determine the effect of NANODOX® 1% hydrogel in adult AD patients. The study will be conducted in the UF Health Dermatology Department - Springhill.

Subjects that voluntarily agreed to participate will be consented and enrolled in the study. Qualified subjects will be required to come to UF Dermatology Clinic for at least four visits, approximately 2 weeks apart, with an optional pre-screening (up to 28 days +/- 2 prior to V1) visit if washout is needed and/or to allow subjects to be enrolled in pre-established enrollment dates. Each visit will last approximately 30-60 minutes.

Subjects will be asked to apply NanoDOX® Hydrogel 1% once daily at bedtime for total of four weeks (or until complete clearance) on the chosen target eczematous and adjoining clinically normal (perilesional) area (to cover an area of the size of an index card). NanoDOX® Hydrogel 1% will be provided to the patient in single dose package containing 1.5 cc of hydrogel (equal to 15mg Doxycycline) which is enough to cover a skin area of the size of an index card. Alchem will provide drug for the study at no cost. Of note, for systemic use doxycycline is used at concentration from 100 mg (antimicrobial) twice daily to 40 mg (anti-inflammatory) daily for periods ranging from 14 days to several months. We included non-lesional/perilesional skin to evaluate the safety (e.g. irritant or toxic effects) of the compound on atopic skin, as those subjects have a lower irritancy threshold as is compared to non-atopic subjectsxii. Also, skin barrier impairment (e.g. increase water loss & increase pH) can be already detected in normal

appearing skin in AD subjects. It is our hypothesis that by normalizing the proteases activities, treatment with NanoDOX® Hydrogel will normalize skin barrier integrity.

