### **Data Monitoring**

The study will be monitored in compliance with the relevant parts of 21 CFR and according to the ICH GCP Guidelines.

A Monitor will visit the Study Center on a pre-arranged schedule to monitor adherence to the protocol and to applicable FDA regulations; and the maintenance of adequate and accurate clinical records. A Case Report Form will be completed for every subject that was enrolled to participate in the Study. The Case Report Form (CRF) will be reviewed in detail, for which the Monitor will have access to subject study records, laboratory data, and other source documentation.

Case Report Forms will be completed as information becomes available or within five days of a Study Visit.

Case Report Forms will be reviewed in detail by the Monitor who will make a decision as to their acceptability. If errors or omissions are found in the course of a data audit, or if clarification of data is required, the Case Report Form(s) in question will be corrected by the Investigator or his/her designee. Data Resolution or Query Forms may be generated on omissions or clarifications, to be completed, signed and dated, and maintained as a part of the CRF.

The Principal Investigator or a Sub-investigator will sign and date the indicated places of the Case Report Form. This signature will indicate that thorough inspection of the data therein has been made and will thereby certify the contents of the form.

The procedures outlined in the protocol and case report forms will be carefully reviewed by the Sponsor, Investigator and staff prior to Study Initiation to ensure appropriate interpretation and implementation. No deviations from the protocol shall be made except in emergency situations where alternative treatment is necessary for the protection, proper care and well being of subjects.

Amendments will be submitted to the IRB for their review and approval prior to implementation. When an amendment to a protocol substantially alters the study design or increases potential risk to the study subject, the Informed Consent form will be revised and if applicable, subject's consent to continue participation will again be obtained.

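### The 6-of-15 rule appears to be judged on 15 completers with treated dropouts replaced, so the response rate and the 'promising' verdict may be too high

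*Combined protocol and SAP*

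**What the plan says.** Section 2, under Number of subjects, sets the target as 15 men and women "who are generally healthy except for atopic dermatitis diagnosed by the US Consensus criteria complete this study". It adds: "This may require enrolling up to 30 subjects depending on retention rates and dropouts".

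The statistical paragraph under Secondary Outcomes in section 5 sets the decision rule: "We would consider 6 or more responses (a) in 15 subjects as promising". Response (a) is at least EASI50 by visit 2 or 4, and (b) is the same for EASI75. The paragraph claims power above 96% at a true response rate of 60% or more. For estimation it says that, by exact binomial methods, "we shall obtain point and interval estimates for the fraction of subjects who respond as" (a) or (b). Primary Outcomes likewise refers only to a percentage of subjects.

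No section defines an analysis set. None says whether the denominator is enrolled, treated or completing subjects, or how a treated subject who leaves or has no score is counted. Data Monitoring says "A Case Report Form will be completed for every subject that was enrolled to participate in the Study". That secures data capture but does not set a denominator.

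**The concern.** Section 2 supplies the only group of 15 that the rule could refer to, and it is defined by completion. Read with the rule, the plan replaces dropouts until 15 subjects finish and then counts responses among those 15.

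In a single open-label arm no comparator shares that selection. If people who do badly on the gel are more likely to leave, the result describes those who stayed and not those who used the product. This route is plausible here. The risk section foresees irritation, burning and dryness, and subjects with an abnormal reaction are told to stop the gel until they have spoken to the team.

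Two things are at stake: the only prespecified efficacy decision in the study, and the EASI50 and EASI75 rates, which are listed as primary. Because no denominator is written down, it could also be chosen after the results are known.

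**Working it through.** **Inputs from the documents.** 15 completers and a ceiling of 30 enrolled (section 2); a cut of 6 in 15, a true rate of 60% and power above 96% (section 5, statistical paragraph).

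**Assumptions, not in the documents.** The number treated (20, with 18 and 30 as variants), the true rate among all treated (25%, and 40% for the reverse case), the response rate among leavers, and a two-sided 95% confidence level.

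**1. The plan's own figure.** With X binomial(15, 0.60), P(X ≥ 6) = 0.966. This agrees with the stated power. Cuts of 5 and 7 would give 0.991 and 0.905, so the figure belongs to exactly 15 subjects and a cut of 6.

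**2. Response rate among completers.** Let n be treated, 15 complete, p be the true rate among all treated and r the rate among leavers. The completer rate is

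p_c = (n·p − (n − 15)·r) / 15,

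and the chance of a 'promising' result is P(X ≥ 6) with X binomial(15, p_c).

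| n | p | r | p_c | P(≥ 6 of 15) |
|---|---|---|---|---|
| 20 | 0.25 | 0.25 (no bias) | (5 − 1.25)/15 = 0.25 | 14.8% |
| 20 | 0.25 | 0.10 | (5 − 0.5)/15 = 0.30 | 27.8% |
| 20 | 0.25 | 0 (worst case) | 5/15 = 0.333 | 38.2% |
| 18 | 0.25 | 0 (worst case) | 4.5/15 = 0.30 | 27.8% |
| 20 | 0.40 | 0.60 (leavers do better) | (8 − 3)/15 = 0.333 | 38.2%, against 59.7% with no bias |

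The last row shows that the direction depends on who leaves. It needs responders to leave and then be discarded.

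**3. The same six responders on two denominators** (Clopper-Pearson, 95%). 6/15 = 40% (16% to 68%). If five further treated subjects left without responding, 6/20 = 30% (12% to 54%).

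**4. A cut of 6 cannot be carried to a larger set.** At a true 25%, P(X ≥ 6) is 14.8% with 15 treated, 38.3% with 20 and 79.7% with 30.

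**5. A proportional cut keeps the power.** Take the smallest count that is at least 40% of those treated, since 6/15 = 40%. At a true 60% among all treated, with every response observed, 8/20 gives 97.9%. Over 15 to 30 treated the lowest power is 94.2%, at 7/16.

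**6. What non-responder counting costs.** Suppose the true rate is 60% and 5 of 20 are lost at random before any score. The expected all-treated estimate is 0.60 × 15/20 = 45%. Reaching 8/20 then needs 8 responders among the 15 scored: P(X ≥ 8 | 15, 0.60) = 78.7%, against 96.6% for 6 of 15 completers. With 30 treated and 15 lost, reaching 12/30 needs 12 of 15, which has probability 9.1%.

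**The case against.** The strongest case against has four parts.

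- **The completer reading is an inference.** The rule says subjects, not completers. This stands, and the point is worded accordingly. A reader might infer that the protocol expressly restricts the analysis to completers; it does not. The exact interval is tied to no set at all.
- **The size and sign of the bias are assumed.** This also stands. A reader might take 30 enrolled for 15 completing as a planned 50% loss after treatment, or conclude that the result will be inflated. Neither is supported. Thirty is a ceiling, and some of those losses may precede dosing, since the design runs "with an optional pre-screening (up to 28 days +/- 2 prior to V1) visit if washout is needed". Losses before the first dose do not bias response among the treated.
- **The design limits informative loss.** The study lasts six weeks, rescue is allowed so a flare need not mean withdrawal, and subjects cleared at visit 2 still have a follow-up visit. On the ordinary reading of response by visit 2 or 4, a qualifying visit 2 score already counts, which makes the reverse case in the table strained. All this makes bias less likely, but it does not cover subjects who leave because of irritation or worsening, or who are lost to follow-up.
- **This is a proof-of-concept pilot, and non-responder counting is itself biased downward when loss is unrelated to response.** Both statements are true. The second is why the completer result should be kept as supporting. The first limits the severity, but at 15 subjects a few exclusions can change the verdict.

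**Conclusion.** The concern holds as an unstated denominator, with a plausible but unquantified upward bias. Read together, section 2 and the statistical paragraph judge the rule on 15 completers and replace treated dropouts. If leavers respond less often, the rate and the verdict are too favourable. With an assumed 20 treated and a true 25% among all treated, the chance of a 'promising' result rises from 15% to 28% or 38%, depending on how leavers respond. If leavers respond as often as completers, there is no bias.

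A reader might also infer that the power statement is wrong. It is not: 96.6% is right for 6 of 15 at 60%. What is missing is who the 15 are. This should be fixed before results are seen; it does not undermine the design.

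**What to change.** In the statistical paragraph of section 5:

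1. Estimate (a) and (b), with exact intervals, on every subject who applied at least one dose. Count as responders those with a qualifying visit 2 or visit 4 score, including a visit 2 responder who later leaves. Count all others as non-responders, including those with no score.
2. Report the rate in the 15 completers as a supporting analysis.
3. State in advance which denominator the verdict uses. All treated subjects are preferable: 6/15 when 15 are treated and, when more are treated, the smallest count that is at least 40% of them (8/20, for example). If the sponsor keeps the verdict on 15 completers, say so and show the all-treated rate and interval beside it. Do not apply a cut of 6 to a larger denominator.

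This changes analysis text and requires a record of who took a first dose. It adds no subjects, visits or procedures, and case report forms are already required for everyone enrolled.

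The statistical price is a conservative estimate, lowered by any unscored loss whatever its cause. With heavy loss, the all-treated verdict can miss a gel that works (step 6 of the working). The sponsor should accept that knowingly, and the completer rate is kept for that reason.

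How to count a score reached after rescue treatment in the target area is a separate question that this change does not settle.

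### Safety is the first primary outcome, but its only stated analysis is a qualitative tabulation with no proportion, interval or denominator, although EASI response gets exact binomial estimates

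*Combined protocol and SAP*

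**What the plan says.** Under Primary Outcomes in the section Data Analysis and Data Monitoring, the first item is the safety and tolerability of the gel on both lesional and normal-looking skin. The item then spells out what this covers at the treated lesion: "including pain and dermatologic/skin toxicity (incidence, severity, frequency, duration and causality) in lesional skin at target site". Two of the named dimensions, incidence and frequency, are quantities.

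The statistical text stands at the end of Secondary Outcomes. For efficacy it says: "Using exact binomial methods, we shall obtain point and interval estimates for the fraction of subjects who respond", with response defined as EASI50 or EASI75. For safety it says: "Side effects and baseline characteristics will be tabulated qualitatively".

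Section 2 (Number of subjects) aims for 15 subjects to complete the study and adds: "This may require enrolling up to 30 subjects depending on retention rates and dropouts". Section 3 describes a single-arm, open-label pilot.

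Section 4 covers the recording of adverse events, severity grading, causality and dictionary coding, and it has a pause rule under Stopping Criteria. No section gives an interval for a reaction rate, names a safety analysis set, or states a criterion for calling the gel tolerated.

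**The concern.** One primary outcome is assigned an estimate with its uncertainty. The primary outcome listed first is assigned a table described only as qualitative. The authors have therefore not decided against intervals in general on the ground that this is a pilot. They plan them for response and leave them out for safety.

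At this sample size the omission matters. A small count, or none, looks reassuring on the page while leaving a wide range of true rates open. Section 3 says that atopic skin has a lower irritancy threshold and that perilesional skin is treated in order to evaluate safety, so the local reaction rate is something the study sets out to learn. Section 1 presents the work as a likely first step towards new therapeutics, so later decisions may draw on these data. A reader of the report should be able to see what rates the data leave possible, and for which subjects.

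**Working it through.** **Inputs.** Completers: 15 (section 2). Maximum enrolled: 30 (section 2). Confidence level: the documents give none, so two-sided 95% is assumed. The number treated is not given. If 15 complete, it lies between 15 and 30. It need not reach 30, because consent can be taken at the optional screening visit before any dose.

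**The plan's own figure.** The protocol states no precision for safety. Its only probability is power for efficacy: over 96% to see 6 or more responders in 15 at a true rate of 60%. The exact binomial tail is P(X ≥ 6 | n = 15, p = 0.60) = 0.966, which agrees. The same exact method is now applied to safety.

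**Zero reactions.** The exact (Clopper-Pearson) two-sided 95% upper limit is 1 − 0.025^(1/n).

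| Number treated | Calculation | Upper limit |
|---|---|---|
| 15 | 1 − 0.025^(1/15) | 21.8% |
| 20 | 1 − 0.025^(1/20) | 16.8% |
| 30 | 1 − 0.025^(1/30) | 11.6% |

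A one-sided 95% limit for 0 of 15 is 1 − 0.05^(1/15) = 18.1%, so the level and sidedness need to be stated.

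**Some reactions, 15 treated.** The limits are the 2.5% quantile of Beta(x, n − x + 1) and the 97.5% quantile of Beta(x + 1, n − x).

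| Reactions | Observed | Exact 95% interval |
|---|---|---|
| 1 | 6.7% | 0.2% to 31.9% |
| 2 | 13.3% | 1.7% to 40.5% |
| 3 | 20.0% | 4.3% to 48.1% |

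**Chance of a clean table.** With 15 treated, a true reaction rate of 10% gives no reactions with probability 0.90^15 = 20.6%. A rate of 20% does so with probability 0.80^15 = 3.5%. With 30 treated and a true rate of 10%, the probability is 0.90^30 = 4.2%.

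**Does the pause rule fill the gap?** Its first limb acts once six or more patients have a local side effect graded above moderate. With 15 treated, P(X ≥ 6) is 6.1% at a true rate of 20% and 27.8% at 30%. With 30 treated, it is 57.2% and 92.3%. Whatever its sensitivity, the rule governs conduct during the trial and does not estimate a rate.

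**The case against.** Descriptive safety reporting is usual in a single-arm pilot, and the protocol calls itself a proof of concept. The word qualitatively may mean only by category, or without formal tests. The data for counts will exist: section 4 records the date, severity, resolution and causality of each event, section 3 has irritation, redness, atrophy and telangiectasia noted at each visit, and all adverse events are to be coded for the final report. Once x and n are reported, anyone can compute the interval. The plan also has a numerical pause rule and treats worsening barrier measurements as a possible sign of subclinical irritation.

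Much of this stands, and it rules out three stronger readings that a reader might infer.

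- *The trial cannot answer its first primary question.* The documents do not support this, because a tabulation of the recorded events can produce an incidence.
- *Subjects who leave because of irritation will drop out of the safety table.* The text points the other way. Adverse events are defined as occurring after any use of the product, all of them are coded, and a case report form is required for every enrolled subject. The denominator is unstated, but nothing limits it to completers.
- *The trial will declare the gel safe on a clean table.* No such rule exists. The only declared decision, 6 or more responders in 15, concerns EASI50.

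The objection does not remove the mismatch. A reader can compute the interval only if x and n are both reported, and the plan commits to neither. The protocol already uses the exact method for another primary outcome, so pilot status does not explain why safety is without it.

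**Conclusion.** The point holds as a gap in the stated analysis of a primary outcome. The outcome names incidence, and the plan assigns it no proportion, interval or denominator. At a two-sided 95% level, no reactions would leave a true rate of up to 21.8% possible if exactly 15 are treated, and up to 11.6% if 30 are treated. The 21.8% should not be quoted without those conditions. The figures assume one yes/no outcome per subject, independent subjects and the exact binomial method. The confidence level and the number treated are assumptions, because the documents give neither.

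The change should be made, but the gap does not undermine the study. Neither the efficacy rule nor the collection of safety data is affected.

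**What to change.** Keep the full tabulation of all side effects, and state that it covers local and systemic events by severity, causality and duration, and by lesional and non-lesional skin. Then add:

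> Among all subjects who applied at least one dose, the number and proportion with any local reaction (including pain) and with any severe local reaction will be reported with exact two-sided 95% binomial intervals, and safety conclusions will cite the upper limit.

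The sentence should be added to the tabulation and not replace it. A sentence on local reactions alone would lose systemic events, causality, the lower severity grades and the split by skin type. The items that section 4 lists for the adverse event form do not include the site of the reaction, so check that the form captures it. Primary outcome 1 needs this in any case.

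The cost is one sentence, a little more analysis with a method already in the plan, and a safety statement that will look less favourable. No new patients, visits or procedures are needed.
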